Among survivors found to be underdiagnosed or undertreated (Aim 1), in a randomized controlled design, compare changes in blood pressure, lipid, and blood glucose values from baseline to 1-year between those receiving the intervention (providing clinical results and survivorship care plans [SCPs] to participants and their healthcare providers, supplemented by clinician-led remote counseling sessions with participants to review SCP contents and teach CV risk factor self-management strategies) vs. control (providing clinical results without SCP to participants and their healthcare providers; with delayed access to the intervention).

- *Hypothesis: At the 1-year follow-up home visit, survivors randomized to the intervention arm will have a lower probability of having an undertreated CV risk factor compared with survivors in the control arm.*

3.1.3 Primary Aim 3

Determine barriers among (Aim 2) survivors (at baseline and 1-year: knowledge of

past cancer treatment, self-efficacy, health-related attitudes, medication adherence) and their primary healthcare providers (at 1-year only: knowledge and self-efficacy towards childhood cancer survivorship care) that contribute to undertreatment of hypertension, dyslipidemia, and diabetes.

- *Hypothesis 1: At baseline, underdiagnosis and undertreatment will be associated with lower knowledge, self-efficacy, and medication adherence, as well as a “self-controlling” health attitude among survivors.*
- *Hypothesis 2: At 1-year follow-up, intervention-arm participants will report improved knowledge, self-efficacy, and medication adherence vs. controls; healthcare providers who received the SCP will report improved knowledge and self-efficacy towards CV risk and survivorship care vs. providers of controls.*

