8.1 Baseline Questionnaire

This will include items on: 1) past medical history, 2) current health and medication adherence, 3) lifestyle habits, and 4) attitudes towards healthcare and current mood (**Table 4; Appendix**).

TABLE 4. Components of baseline questionnaire, exclusive of questions on past medical history and lifestyle habits.

*Health-related self-efficacy⁵⁶	10-item (4-point Likert scale) survey (will be reduced to 5-items) that measures perceived ability to set-goals, cope and recover from setbacks. Results have been found to be a strong predictor of subsequent health behavior change. ⁹⁶
*PROMIS anxiety & depression^{57,58}	These domains (adult 4-item survey; all 5-point Likert scale) are of secondary interest. Prior research via a longer instrument (Profile of Mood States) did not show SCPs associated with mood changes or anxiety. ^{50,85}
*Multidimensional Health Locus of Control [MHLC]⁵⁹	18-item survey (6-point Likert scale) will classify participants with regards to their attitudes towards healthcare screening into “worried”, “collaborative” and “self-controlling” typologies, which have been associated with differential likelihoods of obtaining recommended screening in retrospective CCSS analyses. ⁷⁸
*Medication Adherence Scale (MMAS-4)⁶⁰	Well-established 4-item (0=high, 1-2=medium, 3-4=low adherence) instrument initially used to study hypertension, but since validated for other diseases. ¹⁰⁰ Will be administered separately for blood pressure, lipid, and diabetes medications. Secondary analyses will examine adherence by medication burden.

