13.0 STATISTICAL CONSIDERATIONS

13.1 Aim 1 Analytic Plan

Hypothesis: Approximately 60% of participants will have an abnormal CV risk-factor finding that meets clinical intervention thresholds, and among those with abnormalities, 40% will be undertreated and 80% newly diagnosed.

Primary analyses: We will calculate the prevalence of hypertension, dyslipidemia, and diabetes by self-report and by physiologic measurement. We will then calculate the proportions (with exact 95% confidence intervals) of participants who may be underdiagnosed as well as the proportions undertreated (like **Figure 3**). We will calculate the prevalence of directly measured pre-diabetes separately. **Secondary analyses:** We will examine whether rates differ by: sex; current age; time since cancer diagnosis; obese ($BMI \geq 30 \text{ kg/m}^2$) vs. not; health insurance vs. not; recent history of being seen in a dedicated long-term follow-up clinic for survivors vs. not; and lifestyle factors (smoking, low fruit/vegetable intake, low physical activity).

Sample size considerations: Based on prevalence estimates from CCSS surveys and our pilot (**Table 2, Figure 3**), we expect ~60% of high CV risk participants ($n \sim 480$) to have an abnormal CV risk factor measurement; prevalence of individual risk factors ranging 20-40% (less when stratified by underdiagnosis/undertreatment status). With an overall sample $n=800$, we expect reasonable precision for our primary prevalence estimates (**Table 9**). Power to detect differences <10% in secondary analyses may be more limited.

TABLE 9. Estimated power for Aim 1 analyses.		
Prevalence \pm 95% CI	Minimum detectable proportions*	
N=800	N=320:480	N=200:200
5% \pm 1.5%	5% vs. 1/11%	5% vs. 0/14%
20% \pm 2.8%	20% vs. 12/29%	20% vs. 10/33%
50% \pm 3.5%	50% vs. 40/60%	50% vs. 36/64%

*2-sample Fisher's exact test, 80% power, $\alpha=0.05$.

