13.3 Aim 3 Analytic Plan

Hypotheses: 1) at baseline, underdiagnosis & undertreatment are associated with lower knowledge, self-efficacy, and medication adherence (if applicable), as well as a “self-controlling” health attitude among survivors; 2) at 1-year follow-up, compared with the control arm, the intervention arm will be associated with improved knowledge, self-efficacy, and adherence rates among survivors, and improved knowledge and self-efficacy among healthcare providers.

Baseline survivor-specific factors: Using data from all Aim 1 participants, determine whether those underdiagnosed and undertreated at the time of the 1st home visit have lower knowledge (i.e., less accurate recall of prior anthracycline or chest radiotherapy exposures [chi-square test]) and lower health-related self-efficacy [t-test or Wilcoxon rank-sum] compared with those not affected. Similarly, among those who report medications for the CV risk factors of interest, determine whether those undertreated have lower medication adherence (i.e., lower mean MMAS-4 scores [t-test or Wilcoxon

rank-sum]) vs. those not undertreated. Finally, determine if different health-related behavioral attitudes (“worried”, “collaborative” and “self-controlling”)⁶⁹ are associated with differential rates of underdiagnosis and undertreatment [chi-square test]. *A priori*, we hypothesize that the proportion undertreated will be greatest among “self-controlling” survivors vs. “collaborative” and “worried” (least undertreated) survivors. In subanalyses, we will analyze underdiagnosed participants (i.e., newly diagnosed per 1st home visit) separately from those undertreated (i.e., existing diagnosis but not meeting standard therapeutic goals) relative to the referent group (those without any abnormal CV risk factor). We also will use a combined logistic regression model to determine if knowledge, medication adherence, and health-related behavioral attitudes remain associated with underdiagnosis and undertreatment (combined and separately) after multivariate adjustment. Exploratory covariates are similar as before, and include sex, current age, insurance status, healthcare utilization, self-perceived CV risk, and family history of CV disease.

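### The Aim 3 combined logistic model leaves out survivor self-efficacy, one of the four barriers named in baseline Hypothesis 1, so that barrier gets no adjusted estimate

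*Combined protocol and SAP*

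**What the plan says.** Section 3.1.3 (Primary Aim 3) sets out the survivor barriers to be studied: knowledge of "past cancer treatment, self-efficacy, health-related attitudes, medication adherence". Hypothesis 1 in that section says that at baseline "underdiagnosis and undertreatment will be associated with lower knowledge, self-efficacy, and medication adherence", and adds a self-controlling health attitude. Section 13.3 restates the same four.

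Section 13.3 then gives each barrier an unadjusted baseline test. Knowledge and the attitude typologies get chi-square tests. Adherence gets a t-test or Wilcoxon test, restricted to participants who report medication for the conditions of interest. For self-efficacy the question is whether affected survivors have "lower health-related self-efficacy [t-test or Wilcoxon rank-sum] compared with those not affected".

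The one multivariable baseline analysis is a "combined logistic regression model to determine if knowledge, medication adherence, and health-related behavioral attitudes remain associated with underdiagnosis and undertreatment", fitted for the two outcomes together and separately. On the adjustment set the section says: "Exploratory covariates are similar as before, and include sex, current age, insurance status, healthcare utilization, self-perceived CV risk, and family history of CV disease".

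Table 4 in Section 8.1 lists self-efficacy as a scale of its own, which "measures perceived ability to set-goals, cope and recover from setbacks". The attitude typologies come from a different instrument, the 18-item MHLC.

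**The concern.** Section 13.3 uses the combined model to see which barriers hold up once other factors are taken into account. For self-efficacy that question cannot be answered, because the variable is not in the model. Three barriers would be reported with adjusted estimates and the fourth with an unadjusted comparison only, so the four could not be read side by side.

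The protocol does not treat self-efficacy as minor. Table 4 describes it as a strong predictor of later behavior change, Table 10 gives it a detectable difference, and Hypothesis 2 makes it a 1-year outcome.

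There is also a possible second effect. A measured variable that is related both to the outcome and to the other barriers is a confounder of their estimates. Whether self-efficacy is such a variable here is not known from the documents.

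**Working it through.** **1. What is in the model.**

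| Barrier | Hypothesis 1 | Unadjusted test (13.3) | Combined model (13.3) |
|---|---|---|---|
| Knowledge | yes | yes | yes |
| Self-efficacy | yes | yes | **no** |
| Medication adherence | yes | yes | yes |
| Attitude typology | yes | yes | yes |

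Four places might have supplied the missing term, and none does:
- The six covariates named in 13.3 do not include it.
- The earlier lists to which 13.3 refers back (13.1 and 13.2) hold sex, age, time since diagnosis, obesity, insurance and survivor-clinic attendance, with lifestyle factors in 13.1. Self-efficacy is in neither.
- The attitude term is the MHLC typology, a separate instrument in Table 4.
- After the intervention, survivor self-efficacy is compared between arms without adjustment. The only regression that names self-efficacy concerns the providers.

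**2. The plan's own figure for self-efficacy.** Table 10 gives detectable differences of 20%, 26%, 33% and 46% of an SD. Two-sided alpha 0.05 and 80% power are stated under Table 9 and assumed here for Table 10. With MDE = (1.960 + 0.842) × √(1/n₁ + 1/n₂):

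| Groups | MDE (SD) | Stated | Power at stated value |
|---|---|---|---|
| 320:480 | 2.802 × 0.0722 = 0.202 | 0.20 | 79.1% |
| 240:240 | 2.802 × 0.0913 = 0.256 | 0.26 | 81.3% |
| 150:150 | 2.802 × 0.1155 = 0.324 | 0.33 | 81.5% |
| 75:75 | 2.802 × 0.1633 = 0.458 | 0.46 | 80.4% |

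The row reproduces. It describes the unadjusted comparison and is correct for it.

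**3. How much the omission could bias the knowledge estimate.** Inputs from the documents: about 60% affected (480 of 800), and knowledge present in 25% (Table 10, anthracycline self-knowledge). Assumptions: knowledge has no true effect (OR 1), self-efficacy is standardized with log-OR −0.2 per SD, and self-efficacy correlates positively with the trait behind knowledge. The −0.2 is tied to Table 10: for a normal score with equal SDs, a 0.20 SD difference between groups corresponds to exp(−0.20) = 0.82 per SD. The simulation used 1,000,000 subjects.

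| Assumed correlation | Knowledge OR, self-efficacy omitted | Rejection scaled to n = 800 (nominal 5%) |
|---|---|---|
| 0 | 1.01 | 5% |
| 0.1 | 0.97 | 6% |
| 0.2 | 0.93 | 7% |
| 0.3 | 0.90 | 10% |
| 0.4 | 0.87 | 14% |

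With self-efficacy included, the knowledge OR is 0.99 to 1.01 throughout. A separate simulation (400,000 subjects, with an attitude trait added) gave 0.94 at 0.2 and 0.88 at 0.4. A stronger assumed effect, log-OR −0.4, gives 0.88 and 0.77, but nothing in the documents anchors that value.

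**4. Attitude.** With self-efficacy OR 0.82 and no true attitude effect, the omitted-variable OR for the self-controlling attitude is 1.07 and 1.13 at correlations of −0.2 and −0.4, but 0.94 and 0.88 at +0.2 and +0.4. The documents do not give the sign. Adherence was not simulated.

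**5. Precision after adding the term.** Approximate MDE = 0.2022 / √(1 − R²), where R² is the assumed share of self-efficacy explained by the other predictors: 0.202 (R² = 0), 0.213 (0.10), 0.226 (0.20) and 0.242 (0.30) SD at 320:480.

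**The case against.** The gap may be a drafting slip. The covariates are labeled exploratory and the list is open-ended, so the analyst could add self-efficacy. Hypothesis 1 speaks only of association, and its unadjusted test is present and adequately powered. At the one effect size that can be tied to the documents, the possible bias is modest. The ORs of about 0.87 to 1.13 lie well inside what Table 10 can detect for a 25% covariate: 17% gives (0.17/0.83)/(0.25/0.75) = 0.61, and 34% gives (0.34/0.66)/(0.25/0.75) = 1.55.

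Most of this stands, and it limits the consequence. It does not remove the point. The covariate list may be open, but the barriers that the model is to test are a closed list of three. An optional covariate is also not the same as a hypothesized predictor with a reported estimate, and adding it once the data are seen would be a post hoc choice.

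A reader might go further and infer that the effect of self-efficacy will leak into the knowledge and attitude results, so that the conclusions on all four barriers are wrong. The documents do not support that. Bias requires self-efficacy to be related to both the outcome and the other barriers, and neither association is reported. The direction for attitude turns on an unknown sign, and nothing was shown for adherence. An unadjusted result for self-efficacy is also not wrong; it answers a different question. Nor is self-efficacy untested.

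**Conclusion.** The point holds in a limited form. As written, Section 13.3 gives no adjusted baseline estimate for one of the four barriers that Aim 3 sets out to study, and no reason is stated. This follows from the text and needs no simulation.

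Bias in the other barriers' estimates is possible but not established. For a null knowledge effect and a self-efficacy OR of about 0.82 per SD, it ranges from none at correlation 0 to an OR of 0.87-0.88 at correlation 0.4. Both the correlations and the effect size are assumptions. The rejection rates in the working are for n = 800. Any model that contains adherence is limited to participants reporting medications, so its sample will be below 800 and those rates do not carry over directly. The documents give no count for that subset.

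The unadjusted Hypothesis 1 tests, the Table 10 figures, the randomized 1-year comparison of self-efficacy and the Aim 2 analysis do not depend on this model.

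**What to change.** In the Section 13.3 sentence on the combined logistic model, name self-efficacy as a fourth predictor with knowledge, medication adherence and attitudes. Enter the baseline score as a continuous term and report its adjusted OR beside the others. If the omission was intended, state the reason.

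The cost is one model term, using a scale already in the baseline questionnaire. The detectable difference for self-efficacy at 320:480 would be about 0.20 to 0.24 SD for an assumed R² of 0 to 0.30. It would be larger in any model restricted to participants reporting medications. No other analysis or sample-size statement needs to change.

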6.0 SUBJECT RECRUITMENT & REGISTRATION

6.1 Recruitment

A list of eligible patients for Aim 1 will be generated using existing CCSS data. Staff at the CCSS Data Coordinating Center at St. Jude will be responsible for sending out approach packets to these patients (introductory letter, Consent, Healthcare Provider Form, HIPAA, study questionnaire, and upfront honorarium). We will also have the Consent/ Healthcare Provider Form/ HIPAA Form and the study questionnaire available online. For non-responders, St. Jude interviewers will follow-up with phone calls using their standard process. *As part of St. Jude's standard CCSS process for other CCSS activities, participants will have the option of indicating consent by signing the paper form, signing an online consent, or by providing verbal consent to a CCSS St. Jude interviewer.* Similarly, questionnaires can also be completed by interview.

With our 12/2017 protocol modification, we will also pilot alternative approach packets to see if smaller packets that request less of participants upfront can improve accrual. Specifically, in addition to the existing approach process, we will pilot a 2nd process by which we exclude the printed study questionnaire from the approach packet (an option to complete this on-line will still be mentioned in the cover letter). Participants who consent in this fashion but who do not complete the on-line questionnaire will then be sent a paper version. A 3rd process will also be piloted which will feature a tiered consent process by which the initial consent will just be to complete the initial home visit without consenting to the subsequent randomized intervention trial. For those participants who consent in this fashion, after they complete the initial home visit and are found to be eligible for the randomized intervention trial, they will then receive the second consent form that describes the trial. If one of these alternative approach processes results in a substantially higher enrollment rate, that process will then be adopted as our standard approach.

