7.0 TREATMENT PLAN

7.1 Treatment Plan Overview

7.2 Assignment of Study Group

Among those who meet eligibility criteria for primary aim 1 but not primary aim 2, participation will end after the 1st home visit. Similarly, if we adopt a tiered consent process, those who could be eligible for aim 2 but who do not provide consent to the randomized intervention portion of the study, their participation will end after the 1st home visit.

Among participants who meet eligibility for primary aim 2, there will be a computer randomization on a 1:1 basis to intervention: control assignment, with the control group eligible to receive the intervention on a delayed basis (following the 2nd home visit). The study's goal will be to review in-person collected test results in real-time (within 1-2 days of being received at St. Jude) and determine eligibility with randomization assignment the same day. Given the intervention, it cannot be blinded to

either participant or study clinician. Staff who perform the home visits and the study biostatisticians will be blinded to the study group assignment.

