8.0 STUDY PROCEDURES

An overview of study procedures can be found in **Table 3**.

TABLE 3. Summary of required observations.

	Initial home visit	Baseline counseling session	4-month booster	2 nd home visit
Intervention group	Questionnaires* Anthropometrics Blood draw	Goals/Action Plan Call duration Call fidelity	Rating of Action Plan completion	Questionnaires* Anthropometrics Blood draw
Control group	Same as intervention group	-	-	Same as intervention group
Primary healthcare provider(s)	-	-	-	Provider survey Clinical records
Time window to complete	<2 mo of enrollment (max: <6 mo)	<2mo of home visit (max: <3 mo)	3-5 mo from baseline	11-15 mo from 1 st home visit (no max))

*Participants will be asked to complete the questionnaires prior to the scheduling of their home visits.

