Secondary analyses: In case survivors who were newly diagnosed (i.e., underdiagnosed) following their 1st home visit differ in their response to the intervention vs. those previously diagnosed but undertreated, we will examine estimates stratified by diagnosis status at the 1st home visit. For similar reasons, we also will examine estimates if pre-diabetes are excluded. In our primary model, we also will explore whether differences vary by sex, current age, time since cancer diagnosis, obese (BMI ≥ 30 kg/m²) vs. not, health insurance vs. not, and recent history of being seen in a dedicated long-term follow-up clinic for survivors vs. not. We also will explore, among intervention participants, whether action plan scores from the 4-month session are associated with differential undertreatment rates (as a single parameter). Finally, we plan to also compare across the study arms, the measured CV risk factor values from the 2nd home visit separately: 1) average systolic pressure, 2) average diastolic pressure, 3) LDL, 4) triglyceride, 5) blood glucose, and 6) HbA1c. For this subanalysis we will use linear models, adjusting for the value at the 1st home visit as a covariate.

Sample size considerations: Assuming 60% of Aim 1 participants (n=800) meet Aim 2 eligibility with a subsequent conservative 20% drop-out rate, ~380 survivors (190/arm) would have complete data. The study would be 80% powered ($\alpha=0.05$) to detect RRs ≤ 0.88 (i.e., $\geq 12\%$ reduction in the intervention vs. control group) if the prevalence of having an undertreated CV risk factor among controls after the 2nd home visit was 90% (10% reduction from baseline). If controls had an unlikely 50% reduction, we can still detect RRs ≤ 0.71 . Analyses stratified by initial underdiagnosis or undertreatment status (~75-150/arm) will be able to detect RRs ≤ 0.79 to ≤ 0.86 , respectively. Systematic reviews have reported RRs 0.6-0.8 for strategies similar our proposed interventions in the general population.^{64,65} For continuous outcomes (secondary analyses), we will be powered to detect change equaling $\sim 30\%$ of 1 standard deviation, which equates to 5 mmHg systolic blood pressure, 3 mmHg diastolic pressure, 10 mg/dL LDL, 30 mg/dL triglyceride, 10 mg/dL glucose, and 0.3% HbA1c. Differences within these ranges have been reported by others for interventions conducted in the general population.⁶⁶⁻⁶⁸

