Post-intervention analysis: Among Aim 2 participants (and their designated healthcare provider), we will examine the differences between intervention and control groups following the 2nd home visit with respect to 1) survivor knowledge [chi-square test], 2) survivor self-efficacy [t-test or Wilcoxon rank-sum], 3) survivor-reported medication adherence [t-test or Wilcoxon rank-sum], and 4) provider-reported knowledge and self-efficacy [chi-square tests] related to the care of childhood cancer survivors. All analyses will be intent-to-treat and include all survivors and providers with available end points. Subanalyses can stratify these outcomes by initial underdiagnosis vs. undertreatment status. *We also will analyze practice changes over the 1-year intervention period using clinical records.* This includes comparing [chi-square test] whether documentation rates differ across study arms of: 1) any CV-related screening, 2) CV-related interventions [both lifestyle and drug prescriptions], and 3) treatment intensity (**Table 7** earlier). If any survivors share the same healthcare provider, we will apply bootstrap methods to account for the effects of clustering. In secondary analyses, we will determine, via logistic regression adjusting for randomization status, whether providers of survivors who remain undertreated have lower self-reported knowledge and self-efficacy related to the care of childhood cancer survivors vs. providers of survivors no longer undertreated.

Sample size: For covariates assessed at baseline in Aim 3, we will be able to detect differences $\geq 5\%$, RRs $\leq 0.8 / \geq 1.2$, and $\geq 20\%$ of 1 standard deviation (**Table 10**). Among randomized participants (240/arm) and subanalyses (e.g., analyzing undertreatment, underdiagnosis separately: $\sim 75-150$ /arm), detectable differences will be less.

Covariate frequency	Baseline* N=320:480	Post-intervention & subanalyses		
		240:240	150:150	75:75
10% (e.g., primary care provider self-efficacy towards childhood cancer survivorship care ^{27,28})	5%/17% RR 0.5/1.7	3%/20% RR 0.3/2.0	2%/22% RR 0.2/2.2	- /28% RR -/2.8
25% (e.g., MHLC self-controlling or worried typologies ⁶⁹ ; survivor anthracycline self-knowledge ⁷⁰)	17%/34% RR 0.7/1.4	15%/37% RR 0.6/1.5	12%/40% RR 0.5/1.6	8%/47% RR 0.3/1.9

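### Aim 3 compares survivor self-efficacy and knowledge at 1 year without using their pre-randomisation values, and Table 10's 240:240 column allows for no loss to follow-up

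*Combined protocol and SAP*

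**What the plan says.** Section 13.3 (post-intervention analysis) compares the arms after the 2nd home visit on "1) survivor knowledge [chi-square test], 2) survivor self-efficacy [t-test or Wilcoxon rank-sum"], then on medication adherence and on provider outcomes. It names no baseline covariate and no change score. The synopsis lists these arm comparisons as secondary endpoints.

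The survivor measures also exist at baseline. Section 3.1.3 states: "Determine barriers among (Aim 2) survivors (at baseline and 1-year: knowledge of" past treatment, self-efficacy, attitudes and adherence. Providers are measured at 1 year only. The first part of Section 13.3 analyses the baseline values: "Using data from all Aim 1 participants, determine whether those underdiagnosed and undertreated at the time of the 1st home visit have lower knowledge" and lower self-efficacy.

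The baseline questionnaire is meant to precede randomisation. The Table 3 footnote says "Participants will be asked to complete the questionnaires prior to the scheduling of their home visits". Section 7.2 reviews the home-visit results and aims to "determine eligibility with randomization assignment the same day". A late or missing questionnaire is possible under the piloted approach packets in Section 6.1: "Participants who consent in this fashion but who do not complete the on-line questionnaire will then be sent a paper version".

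The plan already adjusts for baseline elsewhere. For the Aim 2 continuous risk-factor values, Section 13.2 says: "For this subanalysis we will use linear models, adjusting for the value at the 1st home visit as a covariate".

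On numbers, Table 10's post-intervention column is 240:240. Section 13.3 restricts the analysis to survivors with available endpoints, and Section 13.2 takes a conservative 20% drop-out, leaving 190 per arm.

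**The concern.** A baseline value of the same measure is usually the strongest single predictor of its 1-year value. It is already being collected, and leaving it out of the arm comparison gives up precision at no saving. The plan uses such a covariate for the Aim 2 continuous values and gives no reason for treating the Aim 3 survivor outcomes differently.

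The second point is the denominator. Sections 13.2 and 13.3 concern the same randomised survivors at the same time point, but Table 10 counts everyone randomised while Section 13.2 counts completers. If Table 10 is read as the sensitivity of the Aim 3 comparison, it promises somewhat more than the plan's own drop-out allowance supports.

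**Working it through.** **Inputs.** From the plan: 240/arm randomised and 190/arm with complete data (Sections 3.4 and 13.2); 87% 1-year retention in the earlier care-plan trial described in Section 2.2, so 240 × 0.87 ≈ 209/arm; Table 10's 26% of 1 SD, 25% vs 15%/37% and 60% vs 47%/72%. Assumed: two-sided 0.05, 80% power and Fisher's exact test, taken from the Table 9 footnote because no footnote to Table 10 appears in the text. Also assumed: a baseline-to-1-year correlation r of 0.3 to 0.7.

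**1. Reproduce Table 10 at 240/arm.** Detectable difference in SD units = (1.960 + 0.8416) × sqrt(2/n) = 2.8016 × sqrt(2/240) = 0.256, against 26% stated. Exact Fisher power solved for 80% gives 25% vs 14.5%/37.2% and 60% vs 46.8%/72.5%, against 15%/37% and 47%/72% stated. The column reproduces with every randomised survivor observed.

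**2. Allow for loss, unadjusted.** Power for 0.26 SD = Φ(0.26 × sqrt(n/2) − 1.96). For proportions, pooled chi-square power = Φ{[d × sqrt(n) − 1.96 × sqrt(2p(1−p))] / sqrt(p1(1−p1) + p2(1−p2))}, where d = p2 − p1 and p is the mean of p1 and p2.

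| n per arm | Detectable SD | Power, 0.26 SD | Power, 25% vs 37% | Power, 60% vs 72% |
|---|---|---|---|---|
| 240 | 0.256 | 81% | 81% | 79% |
| 209 | 0.274 | 76% | 76% | 74% |
| 190 | 0.287 | 72% | 72% | 70% |

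The Fisher detectable proportions at 190/arm are 25% vs 13%/39% and 60% vs 45%/74%.

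**3. Add baseline adjustment for self-efficacy at 190/arm.** With a share m of baselines missing and handled by an indicator, multiply 0.287 by sqrt(m + (1 − m)(1 − r²)).

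| r | Detectable SD, m = 0 | Detectable SD, m = 0.2 | Power for 0.26 SD, m = 0 |
|---|---|---|---|
| 0.3 | 0.274 | 0.277 | 76% |
| 0.5 | 0.249 | 0.257 | 83% |
| 0.7 | 0.205 | 0.224 | 94% |

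The r that restores 0.256 at 190/arm is sqrt[(1 − 190/240)/(1 − m)] = 0.46 for m = 0 and 0.51 for m = 0.2. At 209/arm with complete baselines it is sqrt(1 − 209/240) = 0.36.

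**4. Knowledge, by simulation at 190/arm.** Logistic regression on arm and baseline recall, reported as a standardised risk difference, was applied to Table 10's 12-point gains with 0 to 20% of baselines missing. Two effect patterns were assumed: an equal shift in log-odds, or a gain only among those lacking the knowledge at baseline. Power is 70–77%, 75–83% or 82–93% at a baseline-to-1-year phi of 0.3, 0.5 or 0.7, against 69–73% for chi-square. Rejection under the null stays near 5% (4.5–5.7%).

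**5. Short-scale check.** Table 4 describes self-efficacy as a "10-item (4-point Likert scale) survey (will be reduced to 5-items"). In simulations of a skewed 5-item, 4-point score (shape assumed) at 190/arm, ANCOVA rejected a true null in 4.1–5.5% of trials, so a short skewed scale does not upset the test.

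**The case against.** The strongest reply is that nothing here is an error: follow-up-only t, rank-sum and chi-square tests are unbiased under randomisation, and adjustment is an efficiency choice. That stands. A reader might infer that the Aim 3 comparison is biased or invalid; the documents do not support it.

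A second reply is that 190/arm is an Aim 2 figure, built on home-visit measurements and called conservative. This also stands. Section 8.7 arranges the 2nd home visit after the follow-up questionnaire is completed, so if that order is kept, at least as many survivors will have questionnaire endpoints as home-visit endpoints. It is therefore wrong to read 190/arm as the number the plan expects for Aim 3. But no section supports zero loss, and at 209/arm the detectable difference is still 0.274 SD.

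Third, the gain rests on a correlation that the documents do not give. At 0.3 the recovery is slight (0.287 to 0.274 SD). The denominator point does not depend on it.

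Fourth, Table 10 prints 26% at 240:240 beside 33% at 150:150, so a reader can interpolate, and a null result would be judged from its confidence interval anyway. That limits the weight of the point but does not remove the mismatch.

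**Conclusion.** The point holds as a modest, nearly free improvement to secondary endpoints, together with a sample-size basis that differs between Sections 13.2 and 13.3. Without adjustment, realistic to cautious follow-up gives a detectable self-efficacy difference of 0.27 to 0.29 SD and about 76% to 72% power for Table 10's 0.26 SD. For its 12-point knowledge gains, power is about 74–76% at 209/arm and 70–72% at 190/arm. Adjustment recovers part or all of this, depending on a correlation assumed between 0.3 and 0.7.

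Two wider readings are not supported. Table 10 is not miscalculated: it reproduces at the n it states. Nor does the point carry over to the Aim 2 primary analysis. At the plan's 90% control rate, simulated baseline adjustment there cut the variance of the log relative risk by only about 0–5%. Provider outcomes have no baseline and lie outside the point. So does the main MMAS-4 comparison, whose n is limited to survivors on relevant medication.

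**What to change.** 1. **Self-efficacy.** Make ANCOVA on the baseline score, with robust standard errors, the single pre-specified main analysis. Keep rank-based and unadjusted tests as sensitivity analyses, with no switch based on observed skew.
2. **Knowledge.** For each exposure item (anthracycline, chest radiotherapy), use logistic regression on arm and the matching baseline recall item, reported as a standardised risk difference. Keep chi-square as a sensitivity analysis.
3. **Missing baselines.** Keep every randomised survivor with an endpoint. Where the baseline is missing, or was returned after randomisation, use mean imputation plus a missing indicator, defined identically in both arms.
4. **Table 10.** Add a 190:190 column for survivor knowledge and self-efficacy only, labelled as the 20% drop-out case: 25% vs 13%/39%, 60% vs 45%/74%, and 29% of 1 SD, all unadjusted. If adjusted figures are quoted, state the assumed correlation. Note that MMAS-4 and provider outcomes have their own, different n.
5. **Unchanged.** Leave the provider and main MMAS-4 analyses as planned.

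The cost is a few sentences in Section 13.3 and one added column, with no new data, visits or participants.
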